#### **4.5.2. Exclusion Criteria**

Subjects who meet any of the following exclusion criteria will be excluded from participation in the study:

1. Subjects who cannot discontinue treatment with therapies for the treatment of seborrheic dermatitis prior to the Baseline visit and during the study according to Excluded Medications and Treatments ([Table 1](#)).
2. Planned excessive exposure to treated area(s) to either natural or artificial sunlight, tanning bed, or other LED.
3. Subjects who cannot discontinue to use of strong systemic P-450 cytochrome inhibitors e.g., indinavir, nelfinavir, ritonavir, clarithromycin, itraconazole, ketoconazole, nefazodone, saquinavir, suboxone and telithromycin for two weeks prior to the Baseline visit (Visit 2) and during the study.
4. Subjects with PHQ-8 ( $\geq 18$  years old, inclusive) or modified PHQ-A (adolescents, 12 to 17 years old, inclusive) score  $\geq 10$  at Screening or Baseline visits.
5. Subjects (9-11 years old, inclusive) with a CDI-2 (parent report) raw score  $\geq 17$  for females and  $\geq 18$  for males at Screening or Baseline visits.

6. History of severe depression, suicidal ideation or behavior, Baseline/Screening C-SSRS (for adolescents and adults 12 years old and older) indicative of suicidal ideation or behavior, whether lifetime or recent/recurrent.
7. Previous treatment with ARQ-151 or ARQ-154.
8. Subjects who have received oral roflumilast (Daliresp®, Daxas®), or apremilast (Otezla®) within the past 4 weeks.
9. Known allergies or hypersensitivity to component(s) of the investigational product which includes roflumilast,  
[REDACTED]
10. Known or suspected:
  - a. Severe renal insufficiency as evidenced by calculated creatinine clearance <30 mL/min
  - b. Moderate to severe hepatic disorders (Child-Pugh B or C)
11. Liver function test results that exceed:
  - AST or ALT > 2x ULN
  - Total bilirubin
    - 1.5x ULN or
    - >ULN and  $\leq$ 1.5x ULN and direct bilirubin is >35% of total bilirubin
  - ALP  $\geq$  2x ULN
12. Subjects with active pityriasis/tinea amiantacea.
13. Subjects with a history or a major surgery within 4 weeks prior to Baseline (Visit 2) or has a major surgery planned during the study.
14. Subjects with any serious medical condition or clinically significant laboratory abnormality that would prevent study participation or place the subject at significant risk, as determined by the Investigator.

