### **5.1.9. Children's Depression Inventory 2 (Parent Report)**

The CDI-2 Assessment will be performed according to the Schedule of Assessments ([Section 1.3](#)) for subjects 9-11 years old, inclusive. Subjects 9-11 years old at the time of assent will complete the CDI-2 throughout the study.

The CDI-2 quantifies depressive symptomatology using reports from children/adolescents, teachers, and parents or caregivers. It is recommended for use in initial evaluation and is appropriate when there is a need for an assessment and robust description of a child's depressive symptoms.

This study will use the CDI Parent Report Form. An example of the Parent Report Form is presented in [Appendix 4](#).

A subject with a CDI-2 raw total score of  $\geq 21$  for females and  $\geq 22$  for males should be referred to a mental health professional for evaluation.

A subject with a CDI-2 raw total score of  $\geq 32$  should be referred to a mental health professional, and Investigators in consultation with the mental health professional should consider interruption or discontinuation of the investigational product.

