**Instructions:**  
For each of the statements below, select one response that best describes your observations of your child in the past two weeks.  
Indicate your response for each item by circling the number that best corresponds to your choice. You may change an item response by drawing an 'X' through your original choice and selecting a new response.  
Remember, for each statement, pick one answer that best describes your observations of your child in the PAST TWO WEEKS.

My child	Not at all	Some of the time	Often	Much or most of the time
1. looks sad.	0	1	2	3
2. has wt.	0	1	2	3
3. does not like himself or herself.	0	1	2	3
4. blames himself or herself or others.	0	1	2	3
5. cries or looks tearful.	0	1	2	3
6. is cranky or irritable.	0	1	2	3
7. enjoys being with people.	0	1	2	3
8. thinks that he or she is ugly.	0	1	2	3
9. has to push himself or herself to do schoolwork.	0	1	2	3
10. has trouble sleeping at night.	0	1	2	3
11. looks tired or fatigued.	0	1	2	3
12. seems lonely.	0	1	2	3
13. enjoys school.	0	1	2	3
14. spends time with friends.	0	1	2	3
15. is showing worse school performance than before.	0	1	2	3
16. does what he or she is told.	0	1	2	3
17. has disagreements and conflicts with others.	0	1	2	3

Copyright © 2013 [name] and Multi Health Systems Inc. All rights reserved.  
In the United States, [name]. [name]. In Canada, [name].  
[name], [name]. [contact] (internationally), [contact]. [contact] or [name].

**APPENDIX 5. COLUMBIA-SUICIDE SEVERITY RATING SCALE  
(C-SSRS) BASELINE/SCREENING VERSION**

**COLUMBIA-SUICIDE SEVERITY  
RATING SCALE  
(C-SSRS)**

Baseline/Screening Version

Version 1/14/09

***Posner, K.; Brent, D.; Lucas, C.; Gould, M.; Stanley, B.; Brown, G.; Fisher, P.; Zelazny, J.;  
Burke, A.; Oquendo, M.; Mann, J.***

*Disclaimer:*

*This scale is intended to be used by individuals who have received training in its administration. The questions contained in the Columbia-Suicide Severity Rating Scale are suggested probes. Ultimately, the determination of the presence of suicidal ideation or behavior depends on the judgment of the individual administering the scale.*

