- **WI-NRS 4-point Reduction** = achievement of at least 4-point reduction in average weekly WI-NRS pruritus score at Weeks 2, 4, and 8 compared to baseline, calculated only for subjects with a pruritus score of ≥ 4 at baseline (PRU4-ITT population).

- **Average Weekly WI-NRS Pruritus Score** will be calculated in a 7-day period, see table 3 for the analysis window. A minimum of 4 days of observations are needed to calculate average weekly WI-NRS.
- **DLQI Score** = sum of the 10 questions (individual questions scored as Very much=3, A lot=2, A little=1, Not at all=0, Not relevant=0, Question 7: Yes=3, No=0, with Not relevant recoded to 0; range for score 0 to 30). If 1 item is missing, it is scored as 0 for that item. If 2 or more items are missing, the score should not be calculated.
- **CDLQI Score** = sum of the 10 questions (individual questions scored as Very much=3, Quite a lot=2, Only a little=1, Not at all=0; Question 7: if the last week was school time, the question was scored as Very much=3, Quite a lot=2, Only a little=1, Not at all=0, with Prevented school recoded to 3, and if the last week was vacation, the standard responses apply; range for score 0 to 30). If 1 item is missing, that item is scored as 0. If 2 or more items are missing, the score should not be calculated.
- **PHQ-8** = sum of the 8 questions (individual questions scored as Not at all=0, Several days=1, More than half the days=2, and Nearly every day=3; range for score 0 to 24). If more than 1 item is missing the score should not be calculated. If 1 item is missing the score is calculated as (sum of answered items\*8)/number of answered items.
- **Modified PHQ-A** = sum of the 8 questions (individual questions scored as Not at all=0, Several days=1, More than half the days=2, and Nearly every day=3; range for score 0 to 24). If more than 1 item is missing the score should not be calculated. If 1 item is missing the score is calculated as (sum of answered items\*8)/number of answered items.
- **CDI-2** = total score is calculated as a sum of the 17 questions (individual questions scored as much or most of the time=3, often=2, some of the time=1, Not at all=0; range for score 0 to 51).
  - CDI-2 emotional problem scale is a sum of 9 questions (Q1, Q3-6, Q8, Q10 -12)
  - CDI-2 function problem scale is a sum of 8 questions (Q2, Q7, Q9, Q13-17)

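### SAP 6.1.7 adds four positively worded CDI-2 items in the wrong direction, so the total and the functional scale are wrong as written

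*SAP*

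**What the plan says.** SAP 6.1.7 defines the CDI-2 score: "total score is calculated as a sum of the 17 questions (individual questions scored as much or most of the time=3, often=2", and so on down to 0 for the lowest response. The stated range is 0 to 51. The emotional scale has nine items (1, 3 to 6, 8, 10 to 12). The other scale is given as "CDI-2 function problem scale is a sum of 8 questions (Q2, Q7, Q9, Q13-17"). Neither document states a reversal for any CDI-2 item. The same SAP section does write out reversed codes for Scalpdex Q19, once for the emotions scale and once for the total.

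The parent form in Protocol Appendix 4 prints the codes 0, 1, 2, 3 in the same order for all 17 items. Twelve of the legible items describe a problem. Four do not:

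- item 7: "enjoys being with people"
- item 13: "enjoys school"
- item 14: "spends time with friends"
- item 16: "does what he or she is told"

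Item 2 is not readable in the supplied text.

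The protocol uses the score so that higher is worse. Section 4.5.2 excludes "Subjects (9-11 years old, inclusive) with a CDI-2 (parent report) raw score" at or above 17 (girls) or 18 (boys). Section 5.1.9 attaches referral to "A subject with a CDI-2 raw total score of" at least 21 (girls) or 22 (boys), with a further threshold at 32. SAP 9.6 summarizes observed values and changes from baseline for the total and both scales.

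**The concern.** A problem score must rise when things get worse. Under the SAP's single coding, a child who often enjoys school and sees friends gains points, and a child who stops doing so loses them. All four positive items sit in the functional scale, which has only eight items, so half of that scale works against the other half.

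For ages 9 to 11 the CDI-2 is the only structured mood instrument in the trial: the C-SSRS and PHQ-A start at 12 and the PHQ-8 is for adults. Protocol 2.4.2 names psychiatric events among the known effects of oral roflumilast that this study is meant to detect. SAP 9.6 plans no threshold table, and SAP 14.3 names no CDI-2 listing (although SAP 6.1.8 says in general that collected data are listed). A misdirected score would therefore distort the one planned summary of this measure, including the sign of a change.

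**Working it through.** **Inputs.** Item coding, range and scale membership come from SAP 6.1.7. Item wording comes from Protocol Appendix 4. The positive items are taken as 7, 13, 14 and 16. Because item 2 is unreadable, each main result is repeated on the assumption that it is positive too.

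**The plan's own figure.** 17 items × 3 = 51, and 9 + 8 = 17 with each item used once, so the range 0 to 51 reproduces. It says nothing about direction, because replacing x by 3 − x leaves it unchanged.

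**Error for any child.** A positive item with raw value x should contribute 3 − x but contributes x, an error of x − (3 − x) = 2x − 3. Over four items with raw sum P (0 to 12), SAP total minus reversed total = 2P − 12. This runs from −12 to +12 and is zero only at P = 6. With item 2 also positive it is 2P − 15, with P the sum over five items.

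**Worked response patterns** (SAP rule / with reversal)

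| Pattern | Total | Functional scale | Emotional scale |
|---|---|---|---|
| No problem on any item | 4×3 = 12 / 0 | 4×3 = 12 / 0 | 0 / 0 |
| Worst on every item | 13×3 = 39 / 51 | 4×3 = 12 / 24 | 27 / 27 |
| Positive items at 2, all others at 1 | 13×1 + 4×2 = 21 / 13×1 + 4×1 = 17 | 4×1 + 4×2 = 12 / 4×1 + 4×1 = 8 | 9 / 9 |

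With item 2 also positive, the totals under the SAP rule become 15, 36 and 22 (12×1 + 5×2), against the same 0, 51 and 17. The functional scale is then 15 at best and 9 at worst, so between the extremes it runs backwards.

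**Change from baseline.** Let N be the worsening on the other items and P′ the worsening on the positive items. The correct change is N + P′; the SAP change is N − P′. Their product is N² − P′², so the signs are opposite exactly when |P′| > |N|.

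- Items 7, 14 and 9 each worsen one level: N = 1, P′ = 2. Total and functional scale change by −1 instead of +3.
- Items 7 and 14 and three emotional items each worsen one level: N = 3, P′ = 2. The total changes by +1 instead of +5 (right sign, wrong size). On the functional scale N = 0, so the change is −2 instead of +2.

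**The case against.** The strongest reply is that the scores may be right in practice. The publisher's scoring key is not in the documents, Protocol 5.1.9 calls the Appendix 4 form an example, and values may have been stored already reversed or totalled on a scoring sheet. The table shells, which may carry programming notes, are in a separate document (SAP 15.1). Naming the functional scale a problem scale suggests the right direction was intended. All of this stands as a limit on what can be said about the table actually produced. It does not rescue the SAP text, which maps response labels to numbers and gives one map for all items. If reversal happens elsewhere, the text still misdescribes the derivation and invites a second reversal or none.

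A second reply is that the examples are constructed. That is fair. The middle pattern has a correct total of 17, at the exclusion cut-off for girls and one point below it for boys, so it is not a typical enrolled child. The worst pattern could not have been eligible at baseline. The formula 2P − 12 does not depend on the examples.

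A third reply is that monitoring of individual children used the protocol's raw-score thresholds at the sites, not the SAP derivation. That also stands: nothing shows that any enrolment or referral decision was affected.

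Finally, the summary is descriptive, SAP 9 rules out inferential safety tests, and the number of children aged 9 to 11 is not given. This limits the importance of the point but does not remove it.

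**Conclusion.** The concern holds. SAP 6.1.7 states a rule that gives wrong CDI-2 totals and functional scores if followed on raw item values. The error in the total is 2P − 12 (up to 12 points either way on a 51-point scale), the functional scale cannot separate best from worst functioning, and its change can have the wrong sign. The total's change has the wrong sign only when the positive items move more than all the others together. The emotional scale is correct.

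This rests on two assumptions: that the four items reverse, as their wording implies, and that item values are stored as printed on the form. If item 2 is positive as well, the error reaches 15 points. The consequence is limited to descriptive safety summaries in the youngest age group; efficacy, alpha and power are unaffected. It should be fixed, with medium confidence that the produced table is wrong.

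**What to change.** 1. Read item 2 on the source form, and confirm from the instrument's scoring key which items reverse.
2. Establish whether the database holds raw or already reversed item values.
3. Only if they are raw, recode items 7, 13, 14 and 16 (and item 2 if positive) as 3 minus the value before forming the total and the functional scale. In either case, state the item direction in SAP 6.1.7 so that nothing is reversed twice.
4. Reconcile this scoring with the raw score the sites used for the CDI-2 thresholds in Protocol 4.5.2, 4.8.6, 5.1.9 and 5.9, for which the protocol gives no scoring rule.
5. Describe and justify the change in the clinical study report (Protocol 6.1) and label it as made after unblinding, in line with SAP 10.1.

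A small wording point can be settled in the same edit: the DLQI question 7 rule in SAP 6.1.7 should say how the graded follow-up to a No answer is scored. The general item codes can be read as covering it; a literal reading would lose 1 or 2 points.

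The cost is one check, a sentence or two in the SAP and, if values are raw, a short recode and a rerun of Table 14.3.6. This assumes that item-level answers are in the database locked on 17-May-2022, which the documents do not say. If only totals were entered, the table can only carry a footnote on how the total was scored.

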#### 6.1.8. Data Adjustments/Handling/Conventions

All collected data will be presented in listings. Data not subject to analysis according to this plan will not appear in any tables or graphs but will be included only in the data listings.

All p-values will be displayed in four decimals and rounded using standard scientific notation (eg, 0.XXXX). If a p-value is less than 0.0001 occurs, it will be shown in tables as < 0.0001. Similarly, if a p-value is greater than 0.9999, occurs it will be shown in tables as > 0.9999.

Adverse events will be coded using the MedDRA version 24.1 or above.

Medications will be coded using the World Health Organization Drug Dictionary Enhanced (WHO-DDE) Global B3 version September 2021.

A treatment-related AE is any AE with a relationship to the study drug of possibly, probably, likely, or missing.

For partial AE and medication start dates:

- If the year is unknown, then do not impute the date but assign a missing value.
- If the year is known, but the month or month and day is unknown, then:
  - If the year matches the year of first dose date and the end date (if present) is after first dose date, then impute as the month and day of the first dose date.

- Otherwise, assign 01 January.
- If the year and month are known, but the day is unknown, then:
  - If the month and year match the month and year of the first dose date, then impute as the day of the first dose date.
  - Otherwise, assign 01.

For partial AE and medication end dates:

- If the year is unknown, then do not impute the date but assign as missing value.
- If the year is known, but the month or month and day is unknown, then:
  - If the year matches the year of the last date of the study (date of last contact if subject lost to follow-up; date of completion or early termination otherwise), then impute as the month and day of the last date of the study.
  - Otherwise, assign 31 December.
- If the year and month are known, but the day is unknown, then:
  - If the month and year match the month and year of the last date of the study, then impute as the day of the last date of the study.
  - Otherwise, assign the last day of the month.

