## 6. GENERAL ISSUES FOR STATISTICAL ANALYSIS

### 6.1. Statistical Definitions and Algorithms

#### 6.1.1. Baseline

Baseline is defined as Study Day 1. In general, the last observation recorded before the first dose of study drug will be used as the baseline for all calculations of change from baseline. For assessments where time was recorded, the last observation recorded before the first application of study drug will be used as the baseline observation for all calculations of change from baseline. If the last non-missing assessment is performed on the same date as the first study treatment administration and time is not available, it is assumed that the assessment took place prior to IP application, per study site training, and the assessment will be considered as baseline, except for adverse events (AEs) and medications starting on the first study treatment dose

administration date which will be considered post baseline.

Average weekly baseline WI-NRS is defined as the average of all non-missing scores reported during the last 7 days prior to treatment if at least 4 of 7 evaluable daily WI-NRS questionnaires are available. Daily baseline WI-NRS is defined as the last non-missing assessment prior to the first study treatment.

For subject tolerability assessments, baseline is derived as the last non-missing measurement taken on the day of first application of study drug.

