## **9.9. Concomitant Medication**

Prior and concomitant medications will be summarized descriptively by treatment group, ATC level 4, and preferred term using counts and percentages.

Prior medications will be presented separately from concomitant medications. Medications that started before the first application of IP will be considered prior medications whether or not they were stopped prior to the first application of study drug. Any medications continuing or starting after the first application of study drug will be considered to be concomitant. If a medication starts before the first application of study drug and continues after the first application of study drug it will be considered both prior and concomitant.

Medications will be coded using WHODrug Global B3, version September 2021.

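### The partial start-date rule for known month and year lacks an end-date check, so a record that ended before first dose in that month is given a start after its own end

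*SAP*

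**What the plan says.** SAP 6.1.8 has a block headed "For partial AE and medication start dates" with two branches that can move a start to the first-dose date.

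- Year known, month unknown: the start is moved on the condition "If the year matches the year of first dose date and the end date (if present) is after first dose date". Otherwise it becomes 1 January.
- Year and month known, day unknown: "If the month and year match the month and year of the first dose date, then impute as the day of the first dose date". When the months differ, the start becomes day 01 of its month. The end date is not consulted.

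Three other parts of the SAP use the resulting date.

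- SAP 6.1.1 counts same-day assessments without a time towards baseline, but makes an exception in a sentence split by a page break. The exception opens "except for adverse events (AEs) and medications starting on the first study treatment dose"; after the break it ends "administration date which will be considered post baseline".
- SAP 9.9 says "Medications that started before the first application of IP will be considered prior medications", and also "Any medications continuing or starting after the first application of study drug will be considered to be concomitant".
- SAP 6.1.7 defines a treatment-emergent AE by an onset after the first application of product.

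The protocol's schedule (1.3) collects prior medications from Screening. Serious AEs are collected from consent, other AEs only after the first application (Protocol 5.1.13; SAP Table 1, footnote t).

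**The concern.** Moving an uncertain start to the first-dose date is a reasonable cautious convention while the start could have been on either side of dosing. A recorded end before first dose removes that uncertainty, because the start must also be before dosing. The SAP recognises this in the year-only branch and not in the month-and-year branch. A record with more date information is therefore handled worse than one with less.

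At stake are the prior and concomitant medication tables (14.1.5 and 14.3.9) and, rarely, the timing of a serious AE. Protocol Table 1 requires topical corticosteroids, topical antifungals and medicated shampoos to be stopped 2 weeks before Day 0, so stops in the calendar month of first dose are foreseeable. Such a treatment could leave the prior table and appear as on-study use of a prohibited product.

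**Working it through.** The plan gives no figure to reproduce on this point. The check applies the rule as written.

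**Worked example (assumed dates).** First dose 20 March 2022; start March 2022, day unknown; recorded end 5 March 2022.

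| Rule | Imputed start | Relation to recorded end |
|---|---|---|
| Month and year, as written | 20 March 2022 | 20 − 5 = 15 days after |
| Year-only rule, if the month were also unknown | 1 January 2022 | before |
| Month and year, with an end-date condition | 1 March 2022 | before |

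**All same-month cases.** Take a 30-day month, true start day S, recorded end day E and first-dose day F, with S ≤ E < F.

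- Number of combinations: sum over F = 1 to 30 of F(F − 1)/2 = 29 × 30 × 31 / 6 = 4,495.
- As written, the imputed start is F. Since E < F, start is later than end in 4,495 of 4,495.
- With the condition, the imputed start is day 1. Since E ≥ 1, start is later than end in 0 of 4,495.

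**Classification after imputation.** The start equals the first-dose date.

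- SAP 6.1.1 makes the record post baseline.
- It no longer started before the first application, so it is not prior under SAP 9.9.
- Taken alone, SAP 9.9 does not make it concomitant either: it neither continues past the first application nor clearly starts after it. Read with SAP 6.1.1, it becomes concomitant.

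**When the case can arise for a washed-out treatment.** For a 2-week washout the last permitted use is day F − 14 of the month, which must be at least 1, so F ≥ 15. The whole course must then lie between day 1 and day F − 14. That window is 1 day long at F = 15 and 17 days at F = 31, with mean (1 + 17)/2 = 9 days. By the same arithmetic, a 1-week washout needs F ≥ 8 and a 4-week washout needs F ≥ 29.

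**The case against.** The strongest reply is that very few records qualify. The start day must be unknown, the start must fall in the month of first dose, and the end must precede first dose. Entry requires disease of at least 3 months' duration, so many treatments will have begun in an earlier month; those go to day 01 of that month and correctly stay prior. This stands, and it limits the size of the point.

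The serious-AE route is narrower still. Non-serious AEs before dosing are not collected, serious ones go to the sponsor within 24 hours of awareness, and onset date and time are to be noted (Protocol 5.7.5). A missing onset day should be rare. This stands too.

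It can also be said that important deviations are found by blinded review (SAP 7.2), not from these tables, and that a programmer might use the recorded end to keep the record as prior. The first limits the consequence. The second is not what SAP 6.1.8 instructs, and neither document says that an imputed start may not follow a recorded end.

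The documents do not support four stronger readings that a reader might infer:

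- *That treatment-emergent counts are inflated.* SAP 6.1.7 requires onset after the first application, and an imputed date equal to the first-dose date carries no time. Post-baseline status follows from SAP 6.1.1; treatment-emergent status is unclear.
- *That about 55% of cases are affected.* Days 15 to 31 are 17 of 31 calendar dates on which a 2-week-washout case can arise. That is not a share of subjects or records.
- *That the imputed start is always at least 14 days late.* This holds only for treatments that observed a washout of 2 weeks or more; for other medications the gap can be one day.
- *That efficacy is affected.* No efficacy analysis in the SAP is defined by imputed medication or AE dates.

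**Conclusion.** The rule is wrong as written, and the point is minor. For every record that meets the three conditions, SAP 6.1.8 produces a start later than the recorded end, and the SAP's own definitions then make it post baseline and remove it from the prior category. Whether a medication lands in the concomitant table or in neither depends on how SAP 6.1.1 and 9.9 are combined.

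The documents give no count of partial dates, so the frequency is unknown; that it is small is a judgement from how narrow the conditions are. The worked dates are illustrative, and the washout arithmetic assumes that the stated washout was observed. The effect is confined to the medication tables and, rarely, a screening serious AE.

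**What to change.** In the month-and-year branch of SAP 6.1.8, impute the first-dose day only if the end date is missing or is not before the first-dose date; otherwise assign day 01 of the month. Use the same boundary in the year-only branch, which now requires an end strictly after first dose and so sends a record ending on the first-dose date to 1 January. Add a programmed check that no imputed start is later than a recorded end. State also whether an AE whose imputed onset equals the first-dose date, with no time, counts as treatment-emergent, and say in SAP 9.9 how a medication starting on that date is classed.

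The cost is a clause in each branch, a line of code and a small rerun of the affected tables. The database was locked on 17 May 2022 and unblinded on 19 May 2022 (SAP 1), so the change must be labelled in the study report as a post-unblinding correction, as SAP 10.1 requires for later changes. It uses dates only, not treatment arm.
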